7.7 Data Analysis

Quantitative data analysis

All quantitative data will be managed and analysed using SPSS for Windows version 14.0 (SPSS Inc., 1998). Exploratory data analysis will be initially carried out to establish the distribution of all continuous and categorical variables. Descriptive statistics (means, standard deviations, percentages) will be used to describe the characteristics of the participating centres, the participants and all the main variables of the study. Non-parametric tests (Spearman rank correlation tests and Mann Whitney U tests) will be performed for non-normally distributed continuous variables. Cronbach's alpha (α) coefficients will be determined for the measures that will be used in the study (i.e., MQOL, MCSI, gastrostomy questionnaire) in order to establish their internal consistency.

Continuity corrected Chi-square (χ^2) tests will be performed to determine the difference in the first-month mortality rate and the complication rate following gastrostomy in PEG and PIG/RIG patients. The same tests will be also performed to determine the self-perceived quality of life changes following gastrostomy in PEG and PIG/RIG patients as well as to determine the changes in carer quality of life. Kaplan-Meier survival curves will be used to determine the median survival time from placement of feeding tube, symptom onset and time of diagnosis of the disease in PEG and PIG/RIG patients. Independent samples t-tests will be used to determine the nutritional status changes following gastrostomy in PEG and PIG/RIG patients. Predictors of survival (e.g., respiratory status, site of symptom onset, stage of disease) following gastrostomy will be determined using logistic regression analysis and Cox proportional hazards regressions analysis.

Qualitative data analysis

All the interviews with patients and/or their informal carers will be tape recorded and subsequently transcribed verbatim in full. The data will be analysed according to the Framework approach for qualitative data analysis [64], with the aid of FrameWork (NatCen Ltd., 2009), a dedicated software package developed by the Qualitative Research Unit of the National Centre for Social Research. Framework analysis, which is increasingly becoming accepted in the context of exploratory qualitative health research [65] has the advantage of being grounded or generative as it is based in, and driven by, the original accounts of the participants. Moreover, it constitutes a dynamic, systematic and comprehensive mode of qualitative data analysis as it is open to change during the analysis process and it allows methodical handling and full review of the collected data. In addition, it enables easy retrieval of the original textual material and comparisons between, and associations within, cases to be made. Finally, Framework analysis is accessible to others, due to the well documented analytical process that involves, allowing other researchers to review the whole process and its results [64].

8 Participant Coding and Data Handling

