There are currently no evidence based guidelines for the management of dysphagia in patients with MND [1]. Consequently we hypothesise that practice around the country will vary with regard to indication and method of insertion for gastrostomy for MND patients. We aim to carry out a survey to assess the variation in practice and identify good practice points. The results of the survey will inform the design of the main prospective component of PROGAS.

- ii) *Identify the most appropriate method for gastrostomy insertion in patients with MND.*

The literature is inconclusive with regards to which method of gastrostomy is preferable for patients with MND. We hypothesise that PIG/RIG procedures are safer for patients with MND and will result in reduced one month mortality, in this patient group.

- iii) *Identify the optimal timing for gastrostomy use in patients with MND.*

The American Academy of Neurology Practice Parameter for ALS suggests that gastrostomy insertion should be performed before FVC falls below 50% [2]. However, there are no specific evidence based guidelines on when in the course of MND a gastrostomy should be inserted. We hypothesise that patients undergoing gastrostomy before malnutrition or with early dysphagia symptoms will have an improved survival compared to patients who have gastrostomy insertion when significant malnutrition and dysphagia have occurred.

- iv) *Identify the effect on quality of life of gastrostomy.*

The evidence regarding improvement in quality of life following gastrostomy is inconclusive [1]. We hypothesise that gastrostomy feeding is associated with an improvement in quality of life of the patient. We will also assess the quality of life and views of the carers regarding the gastrostomy.

- v) *Identify the effect on nutritional status of gastrostomy.*

The evidence regarding an improvement in nutritional status is inconclusive [1]. We hypothesise that gastrostomy feeding is associated with an improvement in nutritional status.

- vi) *Identify the complication rate associated with the various gastrostomy protocols.*

We hypothesise that the different gastrostomy techniques are associated with differing complication rates such as post procedure infection, respiratory complications, tube displacement, and tube falling out.

5 Nature of Project

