This is a questionnaire designed to relate the outcomes of gastrostomy insertion to health-related quality of life of patients. It is used to identify the complications and difficulties of gastrostomy as well as its interference with family and social life, from the point of view of patients [55]. It will be completed by patients at 3 months post gastrostomy.

B. Qualitative Interview Study

The qualitative component of PROGAS at Sheffield and Leeds involves the conduct of semi-structured interviews with patients, and their informal carers (10 patients and 10 carers per site), in relation to their experience of gastrostomy insertion and its impact on their quality of life. The advantage of including a qualitative component into PROGAS is that it compensates for any preconceived assumptions inherent in the structured questionnaires, and provides interviewees with the opportunity to talk about what is important to them setting their views in context [56]. This component will assess the outcomes of gastrostomy from the perspective of the patients and carers; delineate their concerns, problems and needs; give an insight of how these needs could be addressed to improve care; and enhance our understanding of the factors that are associated with gastrostomy feeding and impact

on the quality of life. Each patient and each carer will take part in one interview at 3 months following gastrostomy.

i) Interviews with patients

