interrogate the data for the effect of these parameters on the primary and secondary outcome measures. Patient and clinician choices will inevitably impact on the timing of gastrostomy but at most centres these will not have a major effect on the type of gastrostomy procedure undertaken. An initial evaluation of the participating centres has demonstrated that most centres perform either only PIG/RIG procedures or only PEG procedures, which will reduce the variability which could potentially be introduced by physicians selecting particular procedures.

The power analysis calculation and the plan for subsequent statistical analysis were facilitated by experienced statisticians at the Research and Development department of the Sheffield Teaching Hospitals NHS Foundation Trust and the Yorkshire and Humber NIHR Research Design Service.

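### A chi-square is named for changes in patient and carer quality-of-life scores, and no named test addresses the hypothesised improvement in quality of life and nutrition

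*Protocol*

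**What the plan says.** Protocol section 7.7 fixes these tests:

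- Mortality and complications: "Continuity corrected Chi-square (χ^2) tests will be performed to determine the difference in the first-month mortality rate and the complication rate".
- Patient quality of life: "The same tests will be also performed to determine the self-perceived quality of life changes following gastrostomy in PEG and PIG/RIG patients".
- Carers, in the same sentence: "as well as to determine the changes in carer quality of life".
- Weight and BMI: "Independent samples t-tests will be used to determine the nutritional status changes following gastrostomy in PEG and PIG/RIG patients".
- A general clause that names no outcome: "Non-parametric tests (Spearman rank correlation tests and Mann Whitney U tests) will be performed for non-normally distributed continuous variables".

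Under section 7.2, MQOL (patients) and MCSI (carers) are completed at baseline and at 3 months. MQOL items run from 0 to 10 (Appendix 7). MCSI has 13 items with three ordered answers each (Appendix 8). Of Gastro-Qu, section 7.2 says: "It will be completed by patients at 3 months post gastrostomy". Table 1 agrees, yet secondary outcome iv in section 7.5 lists that questionnaire among the measures of quality-of-life change.

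Hypothesis iv in section 4 reads: "We hypothesise that gastrostomy feeding is associated with an improvement in quality of life of the patient". Hypothesis v says the same of nutritional status.

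**The concern.** There are three mismatches between what is measured, what is hypothesised and what is tested.

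1. A chi-square compares proportions. Applied to a score change, it needs a cut. The result then depends on where the cut falls, and much of the information in the score is discarded. For any score that turns out non-normal, the general Mann-Whitney clause points to a different test for the same outcome.
2. Hypotheses iv and v are before-after statements. The tests named for patient quality of life and nutrition compare PEG with PIG/RIG. If both groups improved or declined by the same amount, those tests would show no difference and would not address either hypothesis.
3. A questionnaire completed once yields no change.

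At stake are the precision and reproducibility of the patient-experience and carer results. Change in weight, quality of life and carer burden are named comparisons in the study aims (section 2, aim iv).

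**Working it through.** **The plan's own figures.** Section 7.6 gives 442 (minimum) and 504 (expected) patients, both for 30-day mortality. It states no sample size or power for MQOL, MCSI or weight, so there is no figure to reproduce here. I use 504 as the most favourable sample; deaths and unreturned forms before 3 months would reduce it.

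**Assumptions (none is in the protocol).** Normally distributed change, 1:1 groups, two-sided 5%, cut placing 50%, 30% or 20% of patients in one category. The continuity correction is defined for a 2×2 table, so I take two categories.

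**Step 1: information kept by a cut.** For a small shift, efficiency relative to the t-test on the same change is φ(c)²/[p(1−p)], where p is the fraction beyond the cut c and φ is the normal density.

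- p = 0.5: 0.3989²/0.25 = 0.637, a loss of 36%
- p = 0.3: 0.3477²/0.21 = 0.576, a loss of 42%
- p = 0.2: 0.2800²/0.16 = 0.490, a loss of 51%

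**Step 2: power at N = 504 (252 per group), difference 0.25 SD.**

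T-test: 0.25 × √(252/2) − 1.96 = 2.806 − 1.96 = 0.846, so power is 80%.

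Corrected chi-square: power = Φ{[|pA − pB| − 1/n − 1.96√(2p̄(1−p̄)/n)] / √[(pA(1−pA) + pB(1−pB))/n]}, with n = 252. At the median cut the proportions are 0.450 and 0.550. The numerator is 0.0995 − 0.0040 − 0.0873 = 0.0082 and the denominator 0.0443, giving Φ(0.185) = 57%.

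| Cut | Power, t-test | Power, corrected chi-square | N for 80% power, corrected chi-square |
|---|---|---|---|
| 50% | 80% | 57% | 832 |
| 30% | 80% | 53% | 922 |
| 20% | 80% | 45% | 1,090 |

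The t-test needs 504. Efficiency with the correction is therefore 504/832 = 0.61, 504/922 = 0.55 and 504/1,090 = 0.46. At 0.50 SD it is 126/220 = 0.57, 126/246 = 0.51 and 126/292 = 0.43. The loss with the correction thus spans 39% to 57%.

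**Step 3: weight.** With equal variances σ² and baseline-to-follow-up correlation r, a change score has variance 2σ²(1−r) and a baseline-adjusted score σ²(1−r²). The ratio is (1+r)/2, so the change-score t-test loses (1−r)/2: 25% at r = 0.5, 10% at 0.8, 5% at 0.9, 2.5% at 0.95. The r values are assumed, and the formula presumes no systematic baseline difference between groups.

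**Step 4: hypotheses against tests.** Hypotheses iv and v ask whether mean change after gastrostomy is above zero. The patient quality-of-life and nutrition tests in section 7.7 ask whether change differs between methods. No paired or one-sample test is named. Mean change could be +1 in both groups or −1 in both groups, and the between-method difference would be zero either way.

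**The case against.** The strongest reply has five parts.

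- *Cut-points and covariates belong in a SAP that is not shown.* This stands as far as it goes: a missing cut is not itself the finding. The protocol has, however, already fixed the test, and no choice of cut makes it a test on the full score.
- *The Mann-Whitney clause covers these scores.* It is general and names no outcome, while the chi-square sentence is specific. At best the section gives two tests for one outcome.
- *Adjustment is intended.* Section 7.6 promises, for key recorded variables, to "interrogate the data for the effect of these parameters on the primary and secondary outcome measures". That is a fair qualification, but no model is named for quality of life or weight; the regressions in section 7.7 are for predictors of survival.
- *Gastro-Qu cannot have a baseline before the tube exists, and its four-category items suit a contingency table.* Both are true. What remains is a wording error: the result is a 3-month status, not a change.
- *Descriptive means would show a uniform rise or fall.* They would if change itself is summarised, but section 7.7 does not say so and promises no interval for it.

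Some stronger readings are tempting. A reader might infer that about half the information is lost throughout. That needs an off-centre cut, the continuity correction at larger effects, or a baseline-adjusted comparator (median cut at r = 0.5: 0.637 × 0.75 = 0.48), and it is wrong for the weight t-test. A reader might say that this t-test ignores baseline; it analyses changes, so baseline is subtracted and merely not used as a covariate. A reader might say that every planned test is between methods; carer change is not explicitly split by method in section 7.5 or 7.7.

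**Conclusion.** The point holds for secondary outcomes; the primary mortality analysis is unaffected. The named chi-square does not suit MQOL and MCSI change. It costs about 36–51% of the information from the cut, or 39–57% with the continuity correction, under assumed normal scores, equal groups and cuts between 50% and 20%. The exact loss cannot be fixed from the protocol. For weight the loss is modest: 5–10% if r is 0.8–0.9.

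Hypotheses iv and v lack a matching test for patient quality of life and nutrition. This should not be stretched into saying that a before-after test would settle them. There is no comparison group without gastrostomy, so an added estimate describes change in those who survive to the visit and does not show an effect of the procedure. The Gastro-Qu inconsistency is certain but small.

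**What to change.** In section 7.7:

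1. Replace the chi-square for MQOL and MCSI with a comparison of the continuous scores: linear regression of the 3-month score on method and baseline score, or Mann-Whitney on the change if clearly non-normal. Say whether carer change is compared by method.
2. Compare Gastro-Qu as a 3-month score, and reword secondary outcome iv in section 7.5 to match.
3. For hypotheses iv and v, report mean within-patient change in MQOL, weight and BMI with 95% CI in all patients, alongside the proportion who died before the visit. Describe it as change in survivors, not an effect of gastrostomy.

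The cost is wording only, since the baselines are already collected. There is one real drawback. Groups are not randomised, and section 7.6 says most centres use one approach only, so baseline-adjusted and change-score analyses can give different answers. Name one as the main analysis beforehand and report the other as a sensitivity analysis. Adjusting for the baseline score does not remove confounding by centre, and the text should say so.

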Motor neurone disease (MND) is the third commonest adult onset neurodegenerative disorder with an annual incidence of 2 in 100,000 and prevalence of 5-7 in 100,000 [3]. MND causes progressive weakness and wasting of muscles controlling movement, breathing and swallowing due to a degeneration of the innervating motor neurones. The cause of the motor neurone death is unknown and currently there are no effective treatments to prevent progression which on average leads to death with 2-3 years of diagnosis [3]. Evidence suggests that Riluzole, an anti-glutamate drug, slows progression by approximately 3 months [4] and non-invasive ventilation (NIV) has been demonstrated to prolong average survival by up to 7 months [5]. Specialist multidisciplinary clinics provide disease-management and palliative care services aiming to alleviate symptoms, maximise function, and to improve quality of life by means of reducing psychological distress and maintaining the autonomy of patients as long as possible [6-11].

Dysphagia, difficulty in swallowing, is a common problem in patients with MND [12, 13] and can present relatively early on in the disease course in patients with bulbar onset MND. Dysphagia results from weakness of the tongue, muscles of mastication and swallowing, as well as from loss of co-ordination of the chewing and swallowing actions [14]. Patients with severe dysphagia experience malnutrition and dehydration; continued weight loss; distressing choking and coughing on attempts to swallow; slow, prolonged and effortful

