7.1 Plan of Investigation

A. Centre Pathway Review

We have 15 MND centres committed to participating in PROGAS. A provisional survey of the centres has identified that 360 gastrostomies are performed for MND patients in the UK per year. The first component of PROGAS will be to perform a detailed survey of current practice regarding gastrostomy pathways at each centre. A questionnaire will be completed by the director of each centre capturing data regarding indication for gastrostomy, timing, and type of gastrostomy. This survey will highlight current practice, good practice points and will enable refinement of the data analysis plan of the main phase of the study. The centre director will also identify a “local champion” who will assist in recruiting patients and liaise with the central study co-ordinator who will be based in Sheffield.

B. Prospective evaluation of Gastrostomy

Following ethical and research governance approvals, participants will be recruited into PROGAS from all participating sites over a period of 21 months. All centres will be encouraged to maintain their usual practice and protocols for gastrostomy provision.

i) Patient enrolment

The study will be discussed with patients and carers, when a gastrostomy is being considered by the clinical team as part of their normal standard care. Patients and carers will be asked to consent to the study at the time of referral for gastrostomy. We will aim to recruit 504 patients and carers over 21 months. This figure is based on 80% (i.e., the anticipated patient response rate) of the 630 eligible patients seen according to the provisional survey of centres undertaken.

ii) Pre Gastrostomy Patient Evaluation

Once patients are successfully recruited and consented into PROGAS, the local investigator will complete a Pre Gastrostomy Patient evaluation form. This form is designed to capture routine data already being recorded in clinics, including demographic and functional characteristics, nutritional and respiratory status and gastrostomy-related data.

iii) Peri-Procedure Evaluation

Patients will then undergo the gastrostomy procedure. At the end of the procedure, either the local investigator or a member of the team performing the gastrostomy insertion will complete a Peri-procedure evaluation form. This form will capture the details of the procedure as well as any complications that occur during the procedure.

iv) Follow Up Patient Evaluation

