Patients will attend their usual follow up appointments at their centre. Each patient will be followed up over 12 months following gastrostomy. At the visits which coincide nearest with 3 months and 1 year post gastrostomy, follow up evaluation forms will be completed. Data on weight, gastrostomy related complications, ALS-FRS and survival will be collected. At the follow-up visits patients and carers will complete quality of life assessment and carer burden assessments respectively.

v) *Quality of life for patients and carers*

Aspects related to the quality of life of patients, and their carers, following gastrostomy will be assessed with a combination of qualitative and quantitative tools. The qualitative sub-study at Sheffield and Leeds sites will evaluate the gastrostomy experience from the perspective of the patients and their carers. In addition, at baseline and at the following up visits patients and carers at all participating sites will complete quality of life and carer burden assessments respectively, as outlined in the following section.

All forms will be anonymised by the local champion at each site and will be returned to the Sheffield-based PROGAS co-ordinator.

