7.2 Measures, Questionnaires and Interviews

A. Main Study

i) *Centre Pathway Review Form (see Appendix 1)*

This is an initial questionnaire which will be completed by the centre director at each site. It is designed to assess the current clinical practice of gastrostomy insertion in patients with MND at each centre. It will record data with regard to the number of gastrostomies performed; the type of gastrostomies offered and the preferred circumstances for each different type; as well as the decision-making criteria influencing the timing of gastrostomy.

ii) *Pre Gastrostomy Patient Evaluation Form (see Appendix 2)*

This evaluation form, which will be completed by the local champion at enrolment, is designed to capture data already being recorded in the neuromuscular clinic as part of routine clinical care. It will record the following data about a recruited patient:

Demographic and functional characteristics: Demographic and functional characteristics of the patients will be recorded including age, gender, date of onset of MND symptoms, date of MND diagnosis, site of onset of MND, severity of bulbar dysfunction, time since first symptom of significant weakness, weight, and height. A functional rating scale for MND/ALS, the Amyotrophic Lateral Sclerosis Functional Rating Scale – Revised (ALSFRS-R) [52] will also be completed (see Appendix 6). These data are available in each patient's medical records.

Measures of respiratory function: Forced vital capacity (FVC); Sniff Nasal Inspiratory Pressure (SNIP); and arterial blood gas or non-invasive measurement of P_{tO_2} - P_{tCO_2} , will be recorded. These parameters of respiratory function are measured routinely in the neuromuscular clinic as part of routine clinical care.

Indices of disease progression: Weight measurement and the ALSFRS-R score will be recorded for each patient. These parameters of disease progression are also measured routinely in the neuromuscular clinic as part of routinely clinical care.

Gastrostomy-related data: The pre-procedure evaluation form will also record data for each patient with regard to gastrostomy indication; type of gastrostomy preferred and preference reasons; potential benefits of gastrostomy; and, patient's influence on the timing of gastrostomy.

iii) Peri-procedure Patient Evaluation Form (see Appendix 3)

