7.4 Participants and Recruitment

Inclusion & Exclusion Criteria

Patients, and their carers, will be recruited locally at the participating centres. Patients with MND will be eligible when a decision has been made to refer the patient for a gastrostomy, regardless of indication.

Patient Inclusion Criteria:

- i) A diagnosis of definite, probable, laboratory supported or possible MND, as defined by the revised El-Escorial criteria
- ii) A decision has been taken to refer the patient for a gastrostomy

Patient Exclusion Criteria:

- i) Contradiction to gastrostomy
- ii) Patient declines gastrostomy

Carer Inclusion Criteria:

- i) Being the main carer of an MND patient who has been referred for a gastrostomy placement.

Carer Exclusion Criteria:

- i) Patient declines to participate in an interview (only for the qualitative component of PROGAS)

Participant Recruitment

Patients and their carers will be recruited at each of the participating sites. A typical site (Sheffield Care and Research Centre for Motor Neurone Disorders), serving a population of approximately 2.2million undertakes approximately 16 gastrostomies per year for patients with MND. With the inclusion of 18 sites, and anticipating an 80% participant response rate, we estimate that we will recruit at least 504 patients over a 21-month recruitment period.

Patients and carers will be informed of the study after a decision to refer for a gastrostomy has been made by a member of the research team. Patients and carers who are not interested will not be contacted again for this study. A patient information sheet, explaining the details of the study, will be given to interested patients meeting all the inclusion criteria and none of the exclusion criteria and a carer information sheet will be given to interested carers. They will be asked to contact the local researcher if they would like to participate in the study. One follow up call will be made by a member of the research team, to initially interested patients and carers who do not contact the local researcher, approximately two weeks following the invitation. Patients and carers who respond negatively to the follow up call will not be contacted again for this study. Patients and carers who contact the local researcher and those who respond positively to the follow up call will be asked to provide their consent for participation in the study.

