7.5 Study Outcomes

Primary:

- i) *Difference in the mortality rate in the first month following gastrostomy in PEG and PIG/RIG patients.*

Secondary:

- i) *Difference in the complication rate (classified in groups according to seriousness and time of occurrence) following gastrostomy in PEG and PIG/RIG patients.*
- ii) *Median survival time from (a) placement of feeding tube, (b) symptom onset, and (c) time of diagnosis of the disease in PEG and PIG/RIG patients.*
- iii) *Nutritional status changes (weight and BMI) following gastrostomy in PEG and PIG/RIG patients.*
- iv) *Self-perceived quality of life changes (measured by MQOL, gastrostomy questionnaire and qualitative interviews) following gastrostomy in PEG and PIG/RIG patients.*
- v) *Change in carer quality of life as measured by MCSI and qualitative interviews.*

Analysis will also include looking into how factors, such as (a) respiratory status, (b) site of symptoms onset, and (c) stage of disease, influence safety and survival following gastrostomy in PEG and PIG/RIG patients.

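### Ordinary Kaplan-Meier medians from symptom onset and diagnosis ignore that patients enter only at gastrostomy, so secondary outcomes ii(b) and ii(c) overstate survival

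*Protocol*

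**What the plan says.** Section 7.5 lists as secondary outcome ii "Median survival time from (a) placement of feeding tube, (b) symptom onset, and (c) time of diagnosis of the disease", separately for the two method groups, PEG and PIG/RIG. Section 7.7 fixes the method: "Kaplan-Meier survival curves will be used to determine the median survival time from placement of feeding tube, symptom onset and time of diagnosis". Neither section mentions delayed entry, left truncation or a landmark.

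Entry comes much later than two of these three origins. Section 7.4 makes this an inclusion criterion: "A decision has been taken to refer the patient for a gastrostomy". Section 7.1 adds: "Patients and carers will be asked to consent to the study at the time of referral for gastrostomy". It also says: "Each patient will be followed up over 12 months following gastrostomy". Section 7.2 has the pre-gastrostomy form record "date of onset of MND symptoms, date of MND diagnosis", and the appended forms also ask for the dates of referral, procedure and death.

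**The concern.** A patient who dies after diagnosis but before referral never enters the study, and one who dies before the procedure has no tube type to be grouped by. The interval from onset or diagnosis to the tube is therefore immortal for everyone analysed. An ordinary Kaplan-Meier estimate from those origins treats patients as at risk throughout it.

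Two things are at stake. The medians would be too long if read as survival with the disease. And if one method is used later in the disease than the other, the later-tubed group carries more immortal time and looks better for that reason alone. The protocol intends its results to feed guidelines on method.

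**Working it through.** The protocol states no median, hazard ratio or power for this outcome, so there is no figure to reproduce. The check covers direction first, then size.

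**From the protocol:** entry at referral; 12 months of follow-up after gastrostomy; 504 patients (252 per group if split equally, an assumption); and, from section 6, a disease that "on average leads to death with 2-3 years of diagnosis".

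**Assumed:** the survival distribution, its median, the time to gastrostomy, and independence of that time from later survival.

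**1. Direction.** Let patient *i* enter at G_i and leave by death or censoring at t_i. At a death time x with d deaths:
- ordinary risk set R(x) = number with t_i ≥ x
- delayed-entry risk set R*(x) = number with G_i < x ≤ t_i

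R* is a subset of R, so 1 − d/R ≥ 1 − d/R* at every death time. The ordinary curve can never lie below the delayed-entry curve. This needs no assumed figures.

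**2. A rough size by hand.** Take exponential survival with true median 18 months. Median survival after the tube is then 18 months whenever the tube is placed, so the ordinary median is roughly the typical wait plus 18. Tube windows of 0–12 and 6–18 months after diagnosis have midpoints 6 and 12, giving about 6 + 18 = 24 and 12 + 18 = 30 months. Simulation gave 23.8–24.0 and 29.6–29.9. The true median is 18 in both groups, so the gap of about 6 months is false.

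**3. Size over a grid.** Weibull survival with shape 1.0, 1.3 or 2.0 and true median 24, 30 or 36 months; log-normal time to gastrostomy with median 6 to 24 months and log-SD 0.5; censoring 12 months after the tube. For shape 1.3 and true median 30 months:

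| Median time to tube | Ordinary KM | Excess | Tubed patients, uncensored | Delayed-entry KM |
|---|---|---|---|---|
| 6 | 34.3 | 4.3/30 = 14% | 33.3 | 30.5 |
| 12 | 39.8 | 9.8/30 = 33% | 37.9 | 31.1 |
| 18 | 45.7 | 15.7/30 = 52% | 42.1 | 30.5 |
| 24 | 51.5 | 21.5/30 = 72% | 46.4 | 32.7 |

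The extremes of the grid are 37.8 against a true 36 (1.8/36 = 5%; shape 2.0, tube at 6 months) and 54.1 against a true 24 (30.1/24 = 125%; shape 1.0, tube at 24 months).

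**4. Between methods, identical true survival, 252 per group.** Rejection by a log-rank test at 5%; shape 1.3, true median 30 months, 200 replicates:

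| Median time to tube, two groups | Ordinary | Delayed entry |
|---|---|---|
| 18 and 18 | 2.5% | 3% |
| 18 and 20 | 8% | 6.5% |
| 18 and 21 | 20% | 6% |
| 18 and 24 | 42.5% | 3.5% |
| 15 and 24 | 76.5% | 7.5% |

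At 18 and 24 months the ordinary medians were 46.0 and 50.4, in favour of the later group.

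With Weibull shape 1.5, median 24 months and uniform tube windows of 0–12, 0–24 and 0–36 months, a 3-month shift gave 32%, 24% and 17%, and a 6-month shift 84%, 66% and 48%. Further runs with that survival gave 22–28% and 67–86%.

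Monte Carlo error at a true 5% is √(0.05 × 0.95/200) = 1.5 points, so rates of 2.5–7.5% are compatible with the nominal level.

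**5. Limits of delayed entry.** With shape 1.0 the delayed-entry median collapsed to 9.75 (true 24, tube at 18 months) and 14.1 (true 30, tube at 12 months), because a few deaths in tiny early risk sets pull down the whole curve. For the 6–18 month window in step 2 it gave about 24 = 6 + 18 rather than 18. Nobody is observed before month 6, so that median is conditional on surviving to month 6.

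**The case against.** - **The medians may be meant only as a description of patients who reached gastrostomy.** For that group, time before the tube is truly lived, and the charge of inflation is weaker. This stands in part. But with follow-up ending 12 months after the tube, censoring is tied to time of entry, and the ordinary curve overshoots even the tubed patients' own median: 45.7 against 42.1 months in the 18-month row.
- **A reader might infer that the PEG versus PIG/RIG contrast is certainly biased.** The protocol does not support that. It gives no time to gastrostomy by method, and section 7.6 says most centres use only one type. With equal timing there is no false difference. A difference remains plausible: section 6 calls PEG unsuitable at FVC 30–50% of predicted and suggests the radiological methods may suit such patients, and one method per centre does not equalise timing between centres.
- **Section 7.7 names no log-rank test for these curves.** This stands. The rejection rates show how far the curves can separate, not the error rate of a planned test.
- **A reader might also infer that immortal time spoils the timing aim.** Section 4 states: "We hypothesise that patients undergoing gastrostomy before malnutrition or with early dysphagia symptoms will have an improved survival". That exposure is nutritional and swallowing status. The curves from onset and diagnosis are planned by method only, and section 7.7 analyses stage of disease on survival following gastrostomy. No early-versus-late comparison on the affected clocks is planned, so the inference fails. Lead time is the issue there: an earlier tube starts the clock earlier.

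**Conclusion.** The point holds for secondary outcomes ii(b) and ii(c). As written, the plan gives medians that are too long for survival with the disease. That direction rests on the entry rule alone. The range of about 5% to 125% rests on assumed survival and assumed times to gastrostomy.

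Bias between methods is conditional on a difference in timing that the protocol makes plausible but does not quantify. If there is one, the later-tubed group is favoured, with false significance of roughly 17–32% at 3 months and 42–86% at 6 months under the stated assumptions.

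First-month mortality and survival from placement both start at the procedure and carry no immortal time from these origins. The defect therefore touches two of the three clocks in one of five secondary outcomes. It should be corrected, but it does not threaten the main result.

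**What to change.** - Make tube placement the main survival clock, with ordinary Kaplan-Meier curves.
- For onset and diagnosis, use delayed-entry Kaplan-Meier and Cox models with entry at gastrostomy. Entry at consent is an alternative if deaths before the procedure are kept and patients are grouped by the preferred procedure recorded on the pre-gastrostomy form.
- Start both groups' curves at a common landmark time at which risk sets are adequate, and label the medians as conditional on reaching it.
- Report the results as associations among patients who reached gastrostomy. State the assumption that tube timing is independent of later prognosis; it is doubtful, since the recorded indications include marked weight loss and recurrent aspiration.
- For the timing aim, note that survival following gastrostomy is subject to lead time, and interpret it with adjustment for time since onset and baseline severity.

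The cost is wording and analysis only, because the dates are already collected. The price is less precision at early times and medians that no longer describe survival from onset or diagnosis without condition.
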